### **5.11.1. Acceptable Concomitant Medications**

All treatments that the investigator considers necessary for a subject's welfare may be administered at the discretion of the investigator in keeping with the community standards of medical care. All concomitant medication will be recorded on the eCRF, including all prescription, over-the-counter, herbal supplements, and IV medications and fluids. If changes occur during the study period, documentation of drug dosage, frequency, route, and date may also be included on the eCRF.

All concomitant medications received within 28 days before the first dose of study treatment and 42 days after the last dose of study treatment should be recorded. Concomitant medications administered after 42 days after the last dose of study treatment should be recorded for SAEs and AEs as defined in Section 8.

#### **5.11.1.1. Antiviral Therapies**

Antiviral therapies for subjects with HCC with a history of HBV are permitted. The following antivirals have no known drug-drug interactions with pembrolizumab and epacadostat based on metabolism: adefovir, entecavir, lamivudine, telbivudine, and tenofovir.

### 5.12. Restricted Medications and Measures

- Systemic steroids may be used at doses  $\leq 10$  mg/day prednisone or equivalents or corticosteroids may be used for radiographic procedures.
- Use of coumarin-based anticoagulants (eg, warfarin) is discouraged. Low-dose warfarin (1 mg) is acceptable; however, doses that increase the INR are discouraged and may require dose modification. If an alternative to coumarin-based anticoagulants cannot be used, investigators should follow the guidelines in [Table 11](#) and either closely monitor or closely monitor and reduce the subject’s dose of coumarin-based anticoagulant upon initiating therapy with INCB024360. The INR should be monitored weekly for the first 4 weeks after initiation of therapy and upon discontinuation of INCB024360.

**Table 11: Warfarin Dose Adjustment Recommendation When Initiating Concurrent INCB024360 (Epacadostat) Treatment**

Stable INR	INCB024360 (Epacadostat) Dose		
	$\leq 100$ mg BID	200 mg BID	300 mg BID
INR $\leq 2.5$	Close INR monitoring	Close INR monitoring	Reduce warfarin by ~33%
INR $> 2.5$	Close INR monitoring	Reduce warfarin by 20%-25%	Reduce warfarin by ~33%

### 5.13. Prohibited Medications and Measures

Subjects are prohibited from receiving the following therapies during the screening and treatment periods of this study unless otherwise noted below:

- Any investigational medication other than the study drugs.
- Any anticancer medications, including chemotherapy or biologic therapy other than the study medications.
- Any immunological-based treatment for any reason. (NOTE: Inhaled or topical steroids are allowed, and systemic steroids at doses  $\leq 10$  mg/day prednisone or equivalents or corticosteroid use for radiographic procedures are allowed as described in Section 5.12, and immune suppressants are allowed for treatment for immune toxicities.)
- Radiation therapy or surgery

**Note:** In the presence of a mixed response (some lesions improving or stable and other lesions progressing), radiation therapy or surgery to a symptomatic solitary lesion or to the brain is allowed. No pembrolizumab infusions are permitted during radiation therapy or procedure and epacadostat should be stopped the day treatment begins. Study medications may be resumed as early as 1 week after treatment if the subject’s symptoms are improving and not requiring corticosteroids for management. If study medications are not resumed within 4 weeks of completing treatment, the subject should discontinue study treatment permanently.

- Administration of live attenuated vaccines within 30 days before the first dose of study treatment and while participating in the study is prohibited. Examples of live vaccines include, but are not limited to, the following: measles, mumps, rubella, chicken pox, yellow fever, rabies, BCG, and typhoid vaccine. Seasonal influenza vaccines for injection are generally killed virus vaccines and are allowed; however, intranasal influenza vaccines (eg, FluMist®) are live attenuated vaccines and are not allowed.
- Administration of an injectable influenza vaccine is prohibited during the DLT observation period (ie, 42 days after Cycle 1 Day 1).
- Any MAOI or drug associated with significant MAO inhibitory activity agents is prohibited from 21 days before Day 1 through 2 weeks after the final dose of INCB024360 has been taken (see [Appendix D](#)).
- Any UGT1A9 inhibitor, including: acitretin, amitriptyline, androsterone, cyclosporine, dasatinib, diclofenac, diflunisal, efavirenz, erlotinib, flutamide, gefitinib, gemfibrozil, glycyrrhetic acid glycyrrhizin, imatinib, imipramine, ketoconazole (systemic), linoleic acid supplements, mycophenolic acid, niflumic acid, nilotinib, phenobarbital, phenylbutazone, phenytoin, probenecid, quinidine, ritonavir, sorafenib, sulfapyrazone, valproic acid, and verapamil.

Subjects who, in the assessment by the investigator, require the use of any of the aforementioned treatments for clinical management should be removed from the study. Subjects may receive other medications that the investigator deems to be medically necessary.

The exclusion criteria (Section 3.3) describes other medications that are prohibited during this study. There are no prohibited therapies during the post-treatment follow-up period.

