b Subjects whose biopsies are PD-L1 indeterminate will not be excluded from the study, with the exception as noted in inclusion criterion 10a. They will be enrolled under the PD-L1 low/negative group but will be analyzed separately. This may require additional enrollment into the PD-L1 low/negative group to ensure that 25 PD-L1 low/negative subjects are enrolled. Low/negative is defined as TPS of 0% to 49%.

c These 2 cohorts will use a Simon 2-stage design. These numbers represent the maximum total sample size for each cohort. The actual sample size may be smaller.

d Closing of cohorts before full enrollment will result in fewer than 446 subjects.

For all subjects enrolled in this study (Phase 1 and Phase 2), participation has 5 components:

**Screening:** Up to 28 days.

**Treatment:** The treatment period with the combination therapy (MK-3475 + INCB024360) will continue every 21 days for up to 24 months (35 administrations of MK-3475). After completion of 24 months of combination treatment, the option for treatment with monotherapy INCB024360 is available for up to 12 months for subjects who are receiving benefit from treatment and have not had disease progression or met any criteria for study withdrawal, or they may stop both INCB024360 and MK-3475. **Note:** As of Amendment 10, INCB024360 administration is removed from the regimen for melanoma cohorts (except with medical monitor approval). Ongoing subjects with melanoma will be instructed to stop taking INCB024360 and to continue on MK-3475 alone (for up to the 35 infusions) or to stop treatment if on INCB024360 monotherapy unless medical monitor approval has been received to continue for the Protocol-specified interval (up to 12 months). Treatment with INCB024360 monotherapy and as part of combination therapy during the re-treatment periods is removed for subjects who have not already initiated such treatment. For those subjects who have already initiated INCB024360 monotherapy treatment or re-treatment and who do not have melanoma, treatment is limited to 12 months.

**Safety/Survival Follow-Up:** Safety follow-up visits will occur 42 to 49 days after the last dose of INCB024360 is taken and survival/safety follow-up visit at 90 days after the last dose of INCB024360.

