### **5.4. Duration of Treatment and Subject Participation**

**Note:** As of Amendment 10, the INCB024360 monotherapy, second course (re-treatment), and re-treatment monotherapy periods are removed. The option for INCB024360 monotherapy, re-treatment combination, and re-treatment monotherapy are only available for up to 12 months to subjects who have already initiated those therapies at the time of implementation of this amendment and who do not have melanoma. The last study visit is the safety follow-up visit.

Each subject enrolled in the study will continue receiving combination study treatment in continuous 21-day cycles for up to 24 months (35 administrations of MK-3475). After 24 months of combination treatment, the option for treatment with INCB024360 monotherapy is available for up to 12 additional months for subjects who are receiving benefit from treatment and have not had disease progression or met any criteria for study withdrawal, or they may stop both INCB024360 and MK-3475. Monotherapy treatment is only available for subjects who have already initiated monotherapy at the time of Amendment 10. Medical monitor approval is required for monotherapy INCB024360 treatment beyond 12 months. Subjects who complete 24 months of MK-3475 (35 administrations), continue on monotherapy INCB024360 for up to 12 months or stop both therapies, and later experience disease progression may be considered for re-treatment with the combination for an additional 12 months (17 administrations of MK-3475) followed by the option to continue monotherapy INCB024360 for up to 12 months as long as they are receiving benefit from treatment and have not met any criteria for study withdrawal, or to stop both therapies. If the subject discontinues all study treatment, the treatment period will end, and the subject will enter the follow-up period (see Section 6.4). Study participation is expected to average about 6 months.

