### 5.6.5. Procedures for Subjects Exhibiting Serotonin Syndrome

As noted in Section 1.3, an uncommon risk of IDO1 inhibition is an increase in serotonin levels that could precipitate a cluster of AEs termed SS when administered alone or in combination with other serotonergic agents. This rare syndrome has been associated with some MAOIs and combinations of serotonergic drugs (Boyer and Shannon 2005). Serotonin reuptake inhibitors and serotonin/norepinephrine reuptake inhibitors (SNRIs) are permitted in the study. The following procedures will be implemented if subjects exhibit the signs/symptoms of SS described in Section 7.5.4, including tremor; hyperreflexia; spontaneous, ocular, or inducible clonus; together with agitation, fever, diaphoresis, or muscle rigidity:

- Immediately interrupt INCB024360 and MK-3475 administration.
- Immediately interrupt any SSRI or SNRI administration.
- Provide appropriate medical management of the subject until all signs/symptoms are resolved (eg, IV fluids and/or sympathomimetic amines for hypotension, benzodiazepines for agitation, administration of 5-hydroxytryptamine antagonists such as cyproheptadine).

- If etiologies other than SS are excluded, MK-3475 administration may be resumed unless other AE management guidelines apply for the specific event.
- If subject chooses to remain in the study, restart treatment with INCB024360 after the SSRI or SNRI has been discontinued, no sooner than 5 half-lives have elapsed for the specific SSRI or SNRI in question, and after resolution of signs/symptoms of SS. The SSRI or SNRI dosing MAY NOT be restarted.
- If subject chooses to withdraw from the study, or must restart treatment with SSRI or SNRI, the subject should be scheduled for a follow-up visit. Treatment with SSRI or SNRI may be initiated 2 weeks after resolution of signs and symptoms of SS.

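### Section 5.13's closing sentence lifts every drug prohibition in follow-up and so contradicts the same section's ban on MAO-inhibiting drugs for two weeks after the last epacadostat dose

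*Protocol*

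**What the plan says.** Section 5.13 of the Protocol lists the therapies that subjects may not receive. Its lead-in confines the list to screening and treatment, except where an item says otherwise. The item on MAOIs and drugs with significant MAO inhibitory activity does say otherwise: these are "prohibited from 21 days before Day 1 through 2 weeks after the final dose of INCB024360 has been taken". Appendix D names them and includes meperidine, linezolid and methylene blue alongside the classical MAOIs.

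The section then closes with an unqualified statement: "There are no prohibited therapies during the post-treatment follow-up period".

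Section 5.4 fixes when that period starts: "If the subject discontinues all study treatment, the treatment period will end, and the subject will enter the follow-up period". Section 6.4.1 starts the safety follow-up interval at the end-of-treatment (EOT) visit, for which Table 12 allows a window of 5 days. Amendment 10 discontinued the disease-status and survival follow-up of Sections 6.4.2 and 6.4.3 but kept safety follow-up. The closing sentence therefore still governs a period that remaining subjects will enter.

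**The concern.** One rule restricts a class of drugs for two weeks after the last epacadostat dose. The other says that nothing is restricted once treatment has ended. For a subject who stops both drugs together, the same days fall under both rules.

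The MAO restriction exists because of serotonin syndrome. Section 5.6.5 says: "This rare syndrome has been associated with some MAOIs and combinations of serotonergic drugs". Section 8.9 names MAOIs, meperidine, linezolid and methylene blue as the agents most closely linked to it. Linezolid is an antibiotic and meperidine an analgesic, so either could be wanted at short notice in a patient who has just come off treatment. Section 5.13 itself leads there: it tells the investigator to take off study a subject who needs a listed drug. A subject stopped because linezolid is needed is then inside the two weeks in question, and the last sentence of the section appears to allow the drug at once.

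**Working it through.** The Protocol gives no figure to reproduce. The check compares two time windows.

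Inputs:
- Length of the MAO restriction after the final epacadostat dose: 2 weeks = 14 days (Section 5.13).
- Start of follow-up: when all study treatment is discontinued (Section 5.4), or at the EOT visit (Section 6.4.1).
- EOT visit window: up to 5 days (Table 12). I assume that treatment is discontinued on the day of the final epacadostat dose.

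Let g be the number of days from the final epacadostat dose to the start of follow-up. Then

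overlap = max(0, 14 − g) days.

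| Case | g | Restricted days inside follow-up |
|---|---|---|
| Follow-up starts on the day of the final dose | 0 | 14 − 0 = 14 |
| Follow-up starts at an EOT visit on the last day of its window | 5 | 14 − 5 = 9 |
| Epacadostat stopped two weeks or more before follow-up | ≥ 14 | 0 |

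Who falls in the first two rows? Both drugs stop together on confirmed progression (Table 16), on most Grade 4 drug-related toxicity (Table 6) and under several rows of Table 8. The overlap arises if epacadostat was being taken until then. Under Amendment 10, melanoma subjects on epacadostat monotherapy are told to stop unless the medical monitor approves continuing (Section 5.1.1); for them epacadostat is necessarily the last drug.

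Who falls in the third row? Melanoma subjects who drop epacadostat under Amendment 10 and continue MK-3475 for at least 14 days, and subjects whose epacadostat had already been held for at least 14 days when treatment ended. Section 5.6.2 allows for interruptions longer than two weeks.

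Safety follow-up runs to a visit at 42 to 49 days, so the 14 days end well inside it.

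**The case against.** The best defence is that the section answers the question itself. Its lead-in allows items to set their own duration, the MAO item does so explicitly, and specific text normally prevails over a general closing line. A careful reader of the whole section would probably apply the two weeks. That much stands, and it is a reason to rate the point low. It does not remove the conflict: the lead-in's exception qualifies the lead-in, whereas the closing sentence comes later, speaks directly about follow-up and has no exception.

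It is also fair to say that the risk is small. Section 5.6.5 calls the syndrome rare, and the Amendment 10 summary calls the risk theoretical. The Amendment 8 summary reports 2 of 958 epacadostat subjects (0.2%) with the syndrome or its symptoms, both mild and resolved. Enrollment ended on 17 May 2018.

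A reader might go further and infer that the sentence also overrides two other restrictions. The documents do not support treating either as a demonstrated contradiction.

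- *SSRIs and SNRIs.* Section 5.6.5 says, "Treatment with SSRI or SNRI may be initiated 2 weeks after resolution of signs and symptoms of SS". That is a timing rule for managing one adverse event. These drugs are permitted in the study (Sections 5.6.5 and 8.9) and are not on the Section 5.13 list, so a sentence about prohibited therapies does not reach them.
- *Live vaccines.* Section 5.13 states: "Administration of live attenuated vaccines within 30 days before the first dose of study treatment and while participating in the study is prohibited". A conflict appears only if participation is read through the Synopsis, which counts safety/survival follow-up among its components. The item sits under a lead-in limited to screening and treatment, so the ban may equally have been meant to end with treatment. A day count would not be firm either: the Synopsis times the 90-day contact from the last epacadostat dose, while Table 12 times it from the last dose of study drug.

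**Conclusion.** The closing sentence is wrong as written for MAO-inhibiting drugs. Where epacadostat is taken to the end of all treatment, about 9 to 14 of the 14 restricted days fall in a period in which the text says nothing is prohibited. The range assumes that follow-up starts between the final dose and an EOT visit five days later. With a gap of 14 days or more there is no overlap.

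This is a low-priority patient-safety wording correction. A reader might infer that subjects have been exposed to a barred drug because of it, but the documents show no such case and no misreading by a site. They also do not say how many subjects remain on treatment. No efficacy or safety analysis depends on the sentence.

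**What to change.** Keep the closing sentence of Section 5.13 and add a clause: *except that MAOIs and drugs with significant MAO inhibitory activity (Appendix D) remain prohibited through 2 weeks after the final dose of INCB024360*. Do not add SSRIs/SNRIs or live vaccines to the clause. Separately, the sponsor should confirm whether the live-vaccine item is meant to extend into follow-up; writing that in without asking could impose a stricter rule than intended.

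The cost is one clause, IRB/IEC approval under Section 13.3 at the sites still active, and a notice to those sites. There are no new procedures, visits or subjects. The documents show no Protocol amendment after Amendment 10, and SAP Amendment 4 of 17 May 2019 still rests on it. If none is planned, a clarification to sites with subjects on treatment, stating that the two-week MAO rule governs, would achieve most of the benefit, because it restates a restriction already in the Protocol.

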#### **5.13.1. Supportive Care Guidelines**

Subjects should receive appropriate supportive care measures as deemed necessary by the treating investigator, including, but not limited to, the items outlined below:

- Nausea/vomiting: Nausea and vomiting should be treated aggressively, and consideration should be given in subsequent cycles to the administration of prophylactic antiemetic therapy according to standard institutional practice. Subjects should be strongly encouraged to maintain liberal oral fluid intake.
- Anti-infectives: Subjects with a documented infectious complication should receive oral or IV antibiotics or other anti-infective agents as considered appropriate by the treating investigator for a given infectious condition, according to standard institutional practice.
- Immune-related AEs: See Section 5.6.3 regarding diagnosis and management of adverse experiences of a potential immunologic etiology.
- Management of infusion reactions from MK-3475: Signs and symptoms usually develop during or shortly after drug infusion and generally resolve completely within 24 hours of completion of infusion. [Table 9](#) shows treatment guidelines for subjects who experiences an infusion reaction associated with administration of MK-3475.

## **6. STUDY ASSESSMENTS**

All study assessments will be performed as indicated in the schedules of assessments ([Table 12](#) and [Table 13](#)). If a subject qualifies for re-treatment, all assessments as indicated in [Table 12](#) and [Table 13](#) should be performed. The order of assessments is suggested by the order of mention within the schedules. For instructions on each assessment, see [Section 7](#). The required laboratory analytes are listed in [Table 14](#).

**Table 12: Schedule of Assessments**

**As of Amendment 10, for those subjects remaining on study, procedures are simplified. The Schedule of Assessment tables have been amended, and assessments that are no longer required have been deleted. For subjects who meet Amendment 10 criteria for re-treatment, the following Schedule of Assessments should be followed, except for the screening visit, which does not apply.**

Visit Day (Range)	Screening	Combination, Monotherapy, and Re-Treatment Period b					EOT	Follow-Up	
		C1D1	Weekly for First 6 Weeks (Phase 1 only) b	C2D1	Day 1 All Subsequent Cycles	Every 9-12 Weeks	Discontinuation	Safety Follow-Up	Safety/Survival Follow-Up c
Evaluation/Window	Day -28 to Day -1	Day 1	± 3 Days	± 3 Days	± 3 Days	± 14 Days	+ 5 Days	42-49 Days After Last Dose of INCB024360d (+ 7 Days)	90 Days After Last Dose of Study Drug
ADMINISTRATIVE PROCEDURES									
Informed consent	X								
Inclusion/exclusion criteria	X	X							
Contact IRT	X	X		X	X		X		
Prior medical and cancer history (tumor-specific) e	X								
Concomitant medications review	X	X		X	X		X	X	
Administer INCB024360 in clinic		X							
Administer MK-3475		X		X	X				
CLINICAL PROCEDURES AND ASSESSMENTS									
Comprehensive physical exam	X						X	X	
Targeted physical exam		X		X	X				
ECOG performance status	X						X		
Vital signs and weight (height at screening only)	X	X		X	X		X		
12-lead ECG	X						X		
AE assessment	X	X		X	X		X	X	X
Laboratory assessments	X	X	X	X	X	X	X	X	
Assess for ascites and encephalopathy (subjects with HCC only)	X	X		X	X		X	X	
Esophagogastroduodenoscopy (subjects with HCC only)	X f								

**Table 12: Schedule of Assessments (Continued)**

Visit Day (Range)	Screening	Combination, Monotherapy, and Re-Treatment Period a					EOT	Follow-Up	
		C1D1	Weekly for First 6 Weeks (Phase 1 only) b	C2D1	Day 1 All Subsequent Cycles	Every 9-12 Weeks	Discontinuation	Safety Follow-Up	Safety/Survival Follow-Up c
Evaluation/Window	Day -28 to Day -1	Day 1	± 3 Days	± 3 Days	± 3 Days	± 14 Days	+ 5 Days	42-49 Days After Last Dose of INCB024360d (+ 7 Days)	90 Days After Last Dose of Study Drug
Fresh/archival tissue collection	X g	X g				X h			
Pathology review of tumor tissue	X g					X h			
EFFICACY MEASUREMENTS									
Radiologic tumor assessments i	X					X j	X k		X k
Bone marrow exam l	X l					X l			

- a Treatment cycles are 3 weeks. Imaging should be performed every 9 weeks (63 days ± 5 days) regardless of any treatment delays for the first 2 assessments (Weeks 9 and 18), then every 12 weeks thereafter.
- b Weekly LFTs are only required in Phase 1.
- c Visit may occur through a phone call, email, or visit by the subject or the subject’s caretaker.
- d Subjects must be followed for AEs for 42 to 49 days after the last dose of study drug; however, subjects must be followed for 90 days for SAEs.
- e For RCC: Memorial Sloan Kettering Cancer Center (MSKCC) score; for HCC: CP score, BCLC stage, and HCV/HBV status; for DLBCL: International Prognostic Index score; for gastric cancer: history of *H. pylori* and Epstein Barr virus (EBV).
- f Esophagogastroduodenoscopy will only be required at screening for subjects with HCC to screen for varices. If esophagogastroduodenoscopy has been performed within the past 12 months before first dose of treatment it does not have to be repeated at screening.
- g Archived tissue samples obtained since last treatment may be acceptable per Inclusion Criterion #11. Tissue should be submitted during screening but must be submitted before study drug administration on Cycle 1 Day 1. For subjects in the melanoma primary refractory and relapsed cohorts, fresh baseline tumor tissue is mandatory and confirmed by local pathologist review that sample in fact contains tumor tissue (unless medical monitor approval is received).
- h An optional biopsy can be obtained any time after Cycle 1 Day 14, for safety or with confirmed response or progression. For subjects in the melanoma primary refractory and relapsed cohorts, tumor tissue is mandatory **during Cycle 3 anytime between Days 8 and 15 (Study Days 50 and 57)** and confirmed by local pathologist review that sample in fact contains tumor tissue (unless medical monitor approval is received). If the subject progresses before this timepoint then biopsy should be done at time of progression. Note: If the baseline tumor biopsy was found to be inadequate, the patient should not undergo an on treatment biopsy. Post-progression biopsy can still be optional.
- i Initial tumor imaging will be performed within 28 days before the first dose of study treatment. Scans performed as part of routine clinical management are acceptable for use as the screening scan if they are of diagnostic quality and performed within 28 days before the first dose of study treatment (including PET imaging for subjects with DLBCL).
- j On-study imaging will be performed every 9 weeks (± 5 days) after the first dose of study treatment for the first 2 assessments (Weeks 9 and 18) then every 12 weeks thereafter, should follow calendar days, and should not be adjusted for delays in cycle starts or extension of combination treatment cycle frequencies. The same imaging technique should be used in a subject throughout the study. Per the irRECIST v1.1 used in this Protocol, if imaging shows progressive disease, the imaging assessment should be performed at a minimum of 4 weeks later to confirm progressive disease as described in the Protocol.
- k In subjects who discontinue study drug without confirmed disease progression, a radiological evaluation should be repeated at the time of treatment discontinuation (ie, date of discontinuation ± 4-week window).
- l Bone marrow examination is only required for subjects with DLBCL. Exceptions include: 1) if a recent bone marrow biopsy was performed (within 60 days of Cycle 1 Day 1), a new bone marrow biopsy does not need to be repeated for screening, or 2) if bone marrow involvement is clearly evident or absent per PET/CT it also would not be required at screening. Subsequently, bone marrow biopsy will be performed only to confirm CR or as clinically indicated.

